In this study, all enrolled participants will receive dupilumab injections in a weight/age-tiered dosing regimen for 24 weeks, followed by a 12-week post-treatment observational period at the end of the study intervention.

Brief summary:

This is a multicenter, single-arm, 24-week treatment, Phase 3 PKM16982 study.

The purpose of this study is to investigate the PK and safety of dupilumab in children diagnosed with CSU who remain symptomatic despite the use of H1-antihistamine treatment.

Study details include:

- Screening: 2 to 4 weeks.
- The treatment duration will be 24 weeks.
- Follow-up period: 12 weeks.
- The study duration will be 38 to 40 weeks (including screening and follow-up).
- The number of study visits will be 6.

Screening period:

Prior to screening, participants must be receiving treatment for CSU with a non-sedating H1-antihistamine.

Prior to all screening assessments, the participant and the parent(s)/caregiver(s)/legal guardian(s) must sign and date the Ethics Committee approved informed assent form (IAF) and informed consent form (ICF), respectively. The participant assent should be obtained for all participants ≥ 6 years of age (or above an age determined by the Institutional Review Board [IRB]/Independent Ethics Committee [IEC]).

All participant(s)/parent(s)/caregiver(s)/legal guardian(s) will receive information on the study objective(s) and procedures from the Investigator. If informed consent has been provided, participants will be assessed for inclusion and exclusion criteria. Blood will be collected for clinical laboratory testing and for the analysis of blood biomarkers (mandatory for participants with body weight ≥ 30 kg and optional for participants with body weight ≥ 15 kg and < 30 kg). All assessments to be performed such as vital signs, baseline assessments of urticarial symptoms, Quality of Life (QoL) indices and a complete list of study activities at screening and at the subsequent visits are provided in the flow chart ([Section 1.3](#)).

The duration of the screening period will be 2 to 4 weeks.

Treatment period:

After successful completion of the screening period, participants will begin the treatment period. All participants will be administered dupilumab subcutaneously (SC) at 1 of 4 dose regimens based on the body weight and age at the Screening visit:

- 200 mg every 4 weeks (Q4W) with no loading dose in children with body weight ≥ 5 kg and < 15 kg.

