- 300 mg Q4W with no loading dose in children with body weight ≥ 15 kg and < 30 kg and age ≥ 2 to < 6 years old.
- 300 mg Q4W with an initial 600 mg loading dose in children with body weight ≥ 15 kg and < 30 kg and age ≥ 6 to < 12 years old.
- 200 mg every 2 weeks (Q2W) with an initial 400 mg loading dose in children with body weight ≥ 30 kg and < 60 kg.

It is recommended that participants continue their maintenance H1-antihistamine therapy, either regular or on any dosing schedule. In the setting of a CSU exacerbation, switch to another H1-antihistamine up to 4-fold the licensed dose for CSU is allowed or alternatively, a short course of oral corticosteroids (OCS) may be temporarily given at the discretion of the treating physician. Participants who permanently discontinue the study intervention will be asked and encouraged to return to the study center for all remaining study visits for follow-up.

Post-treatment period:

All participants will complete a 12-week post-treatment Follow-up period without study intervention after completing their treatment period.

Disclosure Statement: This is a single arm treatment study. There will be no masking of study drug for participants or Investigators.

Number of participants:

Depending on their body weight and age, participants will receive 1 of the 4 dose regimens of dupilumab.

The Sponsor estimates that drug concentrations in serum (primary endpoint) can be adequately assessed with approximately 24 enrolled participants with ≥ 8 participants in each of the 2 weight groups (≥ 5 kg to < 30 kg and ≥ 30 kg to < 60 kg). It is expected that a minimum of 8 participants per weight group (≥ 5 kg to < 30 kg and ≥ 30 kg to < 60 kg) and a total of 24 participants are sufficient and adequate to perform PK analysis.

Note: Enrolled participants are all screened participants who have been allocated to an intervention regardless of whether the intervention was received or not.

Intervention groups and duration:

Study intervention(s)

Participants who satisfy the inclusion and exclusion criteria will be assigned to 1 of the following 4 investigational medicinal product (IMP) intervention groups:

- Dupilumab:
 - 200 mg Q4W with no loading dose for participants aged ≥ 2 years to < 12 years weighing ≥ 5 kg and < 15 kg at Visit 2 (V2),
 - 300 mg Q4W with no loading dose for participants aged ≥ 2 years to < 6 years weighing ≥ 15 kg and < 30 kg at V2,

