- 300 mg Q4W with an initial 600 mg loading dose in children aged ≥ 6 to < 12 years weighing ≥ 15 kg and < 30 kg at V2,
- 200 mg Q2W with an initial 400 mg loading dose for participants aged ≥ 2 years to < 12 years weighing ≥ 30 kg and < 60 kg at V2.

Investigational medicinal product

- Dupilumab 300 mg supplied in prefilled syringes.
- Dupilumab 200 mg supplied in prefilled syringes.

Dupilumab

Formulation:

- Dupilumab 300 mg: a 150 mg/mL dupilumab solution in a prefilled syringe to deliver 300 mg in a 2 mL injection.
- Dupilumab 200 mg: a 175 mg/mL dupilumab solution in a prefilled syringe to deliver 200 mg in a 1.14 mL injection.

Route of administration: SC.

Dose regimen:

The dose regimen assigned to participants will be unchanged during the study intervention period; no dose adjustment will be allowed.

- One injection of 200 mg Q4W for children aged ≥ 2 years to < 12 years weighing ≥ 5 kg and < 15 kg at V2 with no loading dose.
- One injection of 300 mg Q4W for children aged ≥ 2 years to < 6 years weighing ≥ 15 kg and < 30 kg at V2 with no loading dose.
- One injection of 300 mg Q4W after an initial loading dose of 600 mg (2 injections of 300 mg) on Day 1 for children aged ≥ 6 years to < 12 years weighing ≥ 15 kg and < 30 kg at V2.
- One injection of 200 mg Q2W after an initial loading dose of 400 mg (2 injections of 200 mg) on Day 1 for children aged ≥ 2 years to < 12 years weighing ≥ 30 kg and < 60 kg at V2.

Noninvestigational medicinal product(s)

It is recommended that participants continue their established standard of care background therapy with a long-acting non-sedating H1-antihistamines. Any dose schedule of H1-antihistamine is permissible (daily, any number of days per week) and participants do not need to be on a stable dose of H1-antihistamine prior to enrollment.

Please refer to [Section 6.8.1](#) for rescue therapy.

Posttrial access to study medication

Not applicable.

Duration of study periods

- Screening period (2 to 4 weeks).
- Study intervention period (24 weeks \pm 3 days).
- Follow-up period (12 weeks \pm 5 days).

Statistical considerations:

- **Sample size calculations**

Approximately 24 participants will be enrolled to study intervention with \geq 8 participants in each of the 2 weight groups (\geq 5 kg to $<$ 30 kg and \geq 30 kg to $<$ 60 kg).

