1.3 SCHEDULE OF ACTIVITIES (SOA)

| Procedure | Screening (14 to 28 days before Day 1) | Intervention Period (24 Weeks) | | | | | Follow-up (12 weeks) |
|---|--|--------------------------------|------|------|-------|---------|----------------------|
| | | Wk 0 (Day 1) | Wk 1 | Wk 2 | Wk 12 | Wk 24 | |
| Visit ^a | 1 | 2 | 3A | 3B | 4 | 5 (EOT) | 6 (EOS) |
| Screening | | | | | | | |
| Informed consent/assent ^b | X | | | | | | |
| Inclusion and exclusion criteria ^c | X | X | | | | | |
| Demographics | X | | | | | | |
| Medical history ^d | X | | | | | | |
| Prior and concomitant medications | X | X | X | X | X | X | X |
| Dispense e-diary/Participant and/or parents/caregiver e-diary training ^e | X | | | | | | |
| Study intervention | | | | | | | |
| IMP administration/ injection administration and observation training | | X ^{f, g} | | | | | |
| IRT attribution treatment | | X | | | X | | |
| Safety^h | | | | | | | |
| Full physical examination ⁱ | X | X | | | X | X | X |
| Vital signs ^j | X | X | | | X | X | X |
| 12-lead ECG ^k | X | | | | | X | X |
| AE reporting, including SAEs | <=====X=====> | | | | | | |
| Laboratory testing | | | | | | | |
| Hepatitis (HBsAg, HBsAb, HBcAb, HCVAb) and HIV Serology ^l | X | | | | | | |
| Pregnancy test: menstruating participants only ^m | Ser | Ur | | | Ur | Ur | Ur |
| Menstruation status | X | X | | | X | X | X |

| Procedure | Screening (14 to 28 days before Day 1) | Intervention Period (24 Weeks) | | | | | Follow-up (12 weeks) |
|--|--|--------------------------------|----------------|----------------|-------|---------|----------------------|
| | | Wk 0 (Day 1) | Wk 1 | Wk 2 | Wk 12 | Wk 24 | |
| Visit ^a | 1 | 2 | 3A | 3B | 4 | 5 (EOT) | 6 (EOS) |
| Hematology (including basophil/eosinophil counts), biochemistry, urine analysis ^{n,o} | X | | | | | X | |
| Participant's report outcome (PRO) | | | | | | | |
| Severity symptoms score questionnaires (PRO): modified UAS7, ISS7, and HSS7 | X ^p Modified UAS7 (includes ISS7 and HSS7 as components), once daily from Visit 1 to Visit 6 | | | | | | |
| QoL questionnaires ^q : C-DLQI and IDQOL | | X | | | | X | |
| Pharmacokinetics and ADA^r | | | | | | | |
| Serum PK samples for dupilumab concentration | | X | X ^s | X ^t | X | X | X |
| Anti-dupilumab antibody | | X | | | X | X | X |
| Biomarkers | | | | | | | |
| Serum Total IgE ^u | | | X | | | X | |

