Abbreviations: ADA = anti-drug antibodies; AEs = adverse events; AESI= adverse event of special interest; C-DLQI = Children's dermatology Life Quality Index; CRP = C-reactive protein; CSU = chronic spontaneous urticaria; ECG = electrocardiogram; eCRF = electronic case report form; E/D = early discontinuation; EOS = End of Study; EOT= End of Treatment; HBcAb = hepatitis B core antibody; HBsAb = hepatitis B surface antibody; HBsAg = hepatitis B surface antigen; HCVAb = hepatitis C virus antibody; HIV = Human Immunodeficiency Virus; HSS7 = hive severity score over 7 days; IDQOL = Infant's dermatitis quality of life index; IgG anti-TPO = immunoglobulin G anti-thyroperoxydase; Ig E = immunoglobulin E; IMP = investigational medicinal product; ISS7 = itch severity score over 7 days; PK = pharmacokinetic; Q2W = every 2 weeks; Q4W = every 4 weeks; PRO = patient report outcome; ; rtPCR = reverse transcription–polymerase chain reaction; SAE = serious adverse event; Ser = serum; TB = tuberculosis; UAS7 = urticaria activity score over 7 days; Ur = urine.

- a Allowed time window of ± 3 days for each visit of treatment period and ± 5 days for the Follow-up visit.
- b Prior to any screening assessments: all participants ≥ 6 years of age (or above an age determined by the Institutional Review Board [IRB]/Independent Ethics Committee [IEC]) and their parent(s)/caregiver(s)/legal guardian(s) will receive information about the study, on study objective(s) and procedures, to the fullest extent possible, in their language and in terms they are able to understand, and must sign and date the IRB/IEC approved Informed Assent Form (IAF) and Informed Consent Form (ICF), respectively.
- c The clinical status of the participant should be rechecked before first dose of study intervention.
- d Medical history, allergic comorbidities history.
- e Training of participants and parents/caregiver regarding completion of diary to record (a) administration of each dose of drug outside the clinic by parent/caregiver for participants; (b) completion of the assessment of participant reported questionnaires for participants aged ≥ 2 years to <12 years.

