- f* 200 mg Q2W regimen of dupilumab after an initial loading dose of 400 mg on Day 1 for participants weighing ≥ 30 kg and < 60 kg, 300 mg Q4W for participants aged ≥ 2 years to < 6 years weighing ≥ 15 kg and < 30 kg with no loading dose, 300 mg Q4W after an initial loading dose of 600 mg on Day 1 for participants aged ≥ 6 years to < 12 years weighing ≥ 15 kg and < 30 kg, and 200 mg Q4W with no loading dose for participants weighing ≥ 5 kg and < 15 kg at Day 1. The planned last dose will be at Week 22 for Q2W injections and Week 20 for QW4 injections.
- g* Regardless of the participant's age, IMP administration may be performed either at study clinic visits, or by a visiting home nurse or by participant (if ≥ 12 years of age)/participants' parent(s)/caregiver(s)/legally authorized representative trained by the Investigator or designee on how to prepare and administer IMP and how to observe the participant after injection. The injection and observation training will be applicable to the participant (if ≥ 12 years of age)/parent(s)/caregiver(s)/legally authorized representative of participants who wish to administer IMP at home. This training will be performed at Day 1 and may also take place later at any visit in the study if participant (if ≥ 12 years of age)/parent(s)/caregiver(s)/legally authorized representative wish to change to do home injection after initially not choosing this. This training must be documented in the participant's study file. In the cases where the participant (if ≥ 12 years of age)/participants' parent(s)/caregiver(s) prefer not to do home injections, home nurse visits may be arranged to administer the IMP according to the planned dose schedule.
- h* Assessments/procedures should be conducted in the following order: patient-reported outcomes, Investigator assessments, safety, and laboratory assessments (including sample collection for ADA, PK, biomarkers), and administration of study drug.
- i* Physical examinations will include skin, nasal cavities, eyes, ears, respiratory, cardiovascular, gastrointestinal, neurological, lymphatic, and musculoskeletal systems.

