- j* Vital signs, including systolic and diastolic blood pressure (mmHg), pulse rate (beats per minute), temperature ($^{\circ}$ C) (same method of temperature measurement should be used during the course of the study), and respiratory rate will be measured in a semi-supine or sitting position after 5 minutes rest. Temperature and pulse rate should be measured at every on-site visit (mandatory on Week 12). Height (cm) will be measured at screening visit (V1) only. Body weight (kg) will be measured at screening visit (V1), Week 12 (V4) and at end of treatment (EOT)/End of Study (EOS) Visits.
- k* 12-lead electrocardiogram (ECG) after at least 10 minutes of rest in supine position (if supine is feasible for the participant). Review should be done at the study center in a timely manner to determine if there are any safety concerns and for clinical management of the participant.
- l* Clinical laboratory testing at screening visit (V1) will include hepatitis B surface antigen (HBsAg), hepatitis B surface antibody (HBsAb), hepatitis B core antibody (HBcAb), hepatitis C virus antibodies (HCVAb), Human Immunodeficiency Virus (HIV) screen (Anti-HIV-1 and HIV-2 antibodies). In case of results showing HBsAg (negative) and HBcAb (positive), HBV DNA testing will be performed and should be confirmed negative prior to enrollment. In case of results showing HCVAb (positive), hepatitis C virus ribonucleic acid (HCV RNA) testing will be performed and should be confirmed negative prior to enrollment. Tuberculosis test will be performed locally if required and results noted in the eCRF. HBV DNA, and HIV and HCV RNA samples for confirmation purpose will only be collected if a confirmation test is requested. The collection will be done during an unscheduled visit onsite.
- m* Urine pregnancy testing should be done monthly in all post-menarche female participants from Visit 2 to Visit 6. If these participants prematurely discontinue the study intervention, the pregnancy testing should continue for at least 12 weeks after the last dose of study intervention. In between visits, starting after Visit 3A or 3B, urine pregnancy tests must be performed at home. For urine pregnancy test performed at home, female participants will have to complete a Home Pregnancy Test Diary. If a female participant starts menstruating during the study, the study center should be contacted in order to supply urine pregnancy dipstick for monthly testing and Home Pregnancy Test Diary.

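### Does it matter that the regimen is tied to Screening weight in some places and Visit 2 weight in others, and that the below-30-kg safety windows name no reference weight?

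*Protocol*

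**What the plan says.** **Regimen assignment.** The synopsis (Treatment period) gives all participants "1 of 4 dose regimens based on the body weight and age at the Screening visit". Protocol 4.1 and SAP 1.1 say the same. The synopsis lists under Study intervention(s) and Dose regimen, eight bullets in all, use the later visit instead, for example "weighing ≥ 5 kg and < 15 kg at Visit 2 (V2". Footnote f of the schedule of activities (SoA) ends with "200 mg Q4W with no loading dose for participants weighing ≥ 5 kg and < 15 kg at Day 1". Day 1 is Visit 2, and the closing phrase may govern that tier alone or all four tiers in the sentence. Once set, the regimen is fixed: "The dose regimen assigned to participants will be unchanged during the study intervention period; no dose adjustment will be allowed".

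**When weight is measured.** SoA footnote j says: "Body weight (kg) will be measured at screening visit (V1), Week 12 (V4) and at end of treatment (EOT)/End of Study (EOS) Visits". Visit 2 is not listed. However, Protocol 8.2.1 includes weight in the physical examination, and the SoA marks a full physical examination at Visit 2.

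**Windows.** Protocol 9.2.1 and SAP 3.1 end the on-treatment period 14 days after the last dose, or 28 days for children below 30 kg. SAP 3.1 ends the treatment-emergent period at 98 days, or 112 days below 30 kg; SAP 3.8 declares the 112 days as a change from the Protocol. SAP 3.5.1 adds the same 14 or 28 days to exposure duration. None says at which visit the weight is taken.

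**The concern.** Two different rules are stated for a dose tier that cannot be changed afterwards. Screening and Visit 2 are 14 to 28 days apart, so a child close to 15 or 30 kg, or about to turn 6, could fall in different tiers under the two rules. No passage says which weight and age the interactive response technology (IRT) uses.

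For the windows, weight is measured again at Week 12, end of treatment and end of study. A programmer who took a later weight could class a child on an every-4-weeks regimen as 30 kg or more. That child's on-treatment period, treatment-emergent period and exposure would each be cut by 14 days. Laboratory tests are scheduled only at Screening and Week 24, so the one scheduled post-baseline laboratory value would drop out of the on-treatment last-value and worst-value summaries. Late adverse events would be tabulated as post-treatment. With 15 children, one reclassified child is visible in a table by regimen.

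**Working it through.** **1. Does the assignment wording feed any analysis?** Under SAP 2, the PK, safety and ADA populations are analysed by intervention received, and ITT by intervention allocated. Both are recorded facts for each child. Neither is re-derived from a weight at Screening or Visit 2, so no planned summary by regimen changes with the rule that was applied. SAP 4 records that enrollment has stopped at 15, so no further child will be assigned.

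**2. Do the windows work on the evident reading?** Both documents define two enrolment weight groups, 5 to below 30 kg and 30 to below 60 kg. Protocol Table 3 and SAP Table 1 give the first group only every-4-weeks (Q4W) regimens and the second only the every-2-weeks (Q2W) regimen. The 28-day and 14-day allowances equal those dosing intervals.

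The last-dose input is footnote f: "The planned last dose will be at Week 22 for Q2W injections and Week 20 for QW4 injections". With study day = 7 × week + 1, the last dose is Day 155 for Q2W and Day 141 for Q4W.

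| | Q2W, 30 kg or more | Q4W, below 30 kg | Q4W read as 30 kg or more |
|---|---|---|---|
| On-treatment end | 155 + 14 = Day 169 | 141 + 28 = Day 169 | 141 + 14 = Day 155 |
| Treatment-emergent end (SAP) | 155 + 98 = Day 253 | 141 + 112 = Day 253 | 141 + 98 = Day 239 |
| Exposure | 154 + 14 = 168 days = 24 weeks | 140 + 28 = 168 days = 24 weeks | 140 + 14 = 154 days = 22 weeks |

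Day 169 is Week 24 and Day 253 is Week 36, the end-of-treatment and end-of-study target days in SAP 5.4. The two groups agree on all three figures only when below 30 kg means the Q4W regimens.

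**3. What would a misreading cost?** For one affected child:

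- With "Allowed time window of ± 3 days for each visit of treatment period", the Week 24 visit falls on Days 166 to 172, after Day 155. The laboratory value leaves the on-treatment last-value and worst-value summaries.
- It stays in the by-visit summary (Days 128 to 211, SAP 5.4) and in the summary of potentially clinically significant abnormalities, which runs over the treatment-emergent period (SAP 3.5.3.1).
- Adverse events starting on Days 240 to 253 move from treatment-emergent to post-treatment.

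**4. How many children could be involved?** The documents give no growth rate or weight distribution, so these inputs are assumptions: growth of 1 to 4 kg a year, and weights spread evenly over either 5 to 30 kg (width 25) or 15 to 30 kg (width 15). SAP 4 implies 7 or 8 of the 15 are below 30 kg.

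- *Growth between Screening and Visit 2:* 1 × 14/365.25 = 0.038 kg to 4 × 28/365.25 = 0.307 kg.
- *Crossing a weight cut-off in that gap:* with width 25, both 15 and 30 kg count: 7 × 2 × 0.038/25 = 0.02 to 8 × 2 × 0.307/25 = 0.20 children. With width 15, only 30 kg counts: 7 × 0.038/15 = 0.02 to 8 × 0.307/15 = 0.16.
- *Turning 6 in that gap (ages spread over 6 to 10 years):* 7 × (14/365.25)/10 = 0.03 to 8 × (28/365.25)/6 = 0.10 children.
- *Passing 30 kg within 168 days:* growth 0.46 to 1.84 kg, so 7 × 0.46/25 = 0.13 to 8 × 1.84/15 = 0.98 children.
- *Passing 30 kg within 252 days (end-of-study weight):* growth 0.69 to 2.76 kg, so 7 × 0.69/25 = 0.19 to 8 × 2.76/15 = 1.47 children.

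The last two lines matter only if someone uses a weight taken during or after treatment.

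**The case for a change.** The strongest case for acting is that the text does contradict itself and nothing in it settles the matter. Footnote j and Protocol 8.2.1 even disagree on whether a Visit 2 weight is scheduled. The general baseline rule, the last value before first dose, does not help: if a Visit 2 weight was recorded, the baseline weight category in SAP 5.3 could differ from a tier set at Screening. The SAP repeats the undefined below-30-kg wording in its own declared change, and wording the windows by dosing interval would cost a few words.

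Most of this is correct as description. The assignment passages conflict and must be reconciled, and so must footnote j with 8.2.1. A mismatch between baseline weight category and tier is possible for a child at a cut-off, but it would show in the demographic table and alter no window or regimen summary. The IRT rule belongs in an operational specification, so its absence here does not show that it was left undefined.

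The part that does not stand is the step to a wrong result. It needs an analyst to ignore the two weight groups used throughout both documents, and the exact match of the allowances to the dosing intervals, in favour of a weight taken after treatment began. Laboratory samples drawn on Days 170 to 172 fall outside the on-treatment period for any on-schedule child on either reading, so they do not bear on this question.

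**Conclusion.** No change to the plan. The Screening and Visit 2 passages contradict each other and must be reconciled in the record of the trial, most simply where the report describes how the IRT assigned regimens. This review takes no view on which visit should govern. With enrollment closed and analyses following the regimen allocated or received, that is documentation and alters no planned result.

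The missing reference weight for the windows is a gap that analysts will fill sensibly. Read as the enrolment weight group, it already gives Day 169, Day 253 and 24 weeks for both dosing intervals, so clearer wording would be expected to change no table. A later weight would shift 14 days for each affected child. The expected number is below one by Week 24 and at most about 1.5 if an end-of-study weight were used. Those counts rest on the assumed growth rates and weight spread; the day arithmetic rests only on the planned last doses and on-schedule dosing.
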